Overall Study Design. For Aims 1 and 2, a prospective, observational study will recruit 100 men and women with chronic low back pain (+/- leg pain) who are scheduled to undergo lumbar spine surgery at the University of Kansas Medical Center (KUMC). 50 will participate in phenotypic characterization and 50 will participate in phenotypic characterization and quantitative sensory testing (QST) procedures. After screening, informed consent, and enrollment into the study, all subjects will undergo an evaluation which includes a comprehensive battery of questionnaires for patient phenotyping that will assess symptoms including pain, physical function, depression, anxiety, and catastrophizing symptoms. QST parameters will only be performed on half of the cohort of lumbar spine surgery patients. Patient phenotyping and QST procedures will take place in one visit pre-operatively. At two weeks, one month, three months, & six months post-surgery, we will administer one questionnaire to determine analgesic response to surgery. This will establish longitudinally-designated post-surgical analgesic outcome groups (see Statistical Analysis section for definitions). Instead of just a three month time point that is often used in analgesic trials, a six month time point was chosen to give adequate time for recovery and response to surgery. Phenotyping and QST will also be done in a cross-sectional manner on 50 age and sex-matched healthy controls and 50 age and sex-matched patients with an established diagnosis of FBSS (established-FBSS) to compare to the longitudinally-designated post-surgical analgesic outcome groups. For Aim 3, 30 men and women with chronic low back pain (+/- leg pain) who are scheduled to have lumbar spine surgery at KUMC will undergo pre-operative functional, structural, and chemical neuroimaging studies. 15 age and sex-matched healthy controls and 15 age and sex-matched established-FBSS patients will also undergo the same neuroimaging studies to compare to the longitudinally-designated post-surgical analgesic outcome groups. Patients for Aim 3 will be recruited from both the prospective and cross-sectional cohorts enrolled for Aims 1 and 2. The goal of the studies in Aim 3 are to investigate whether pre-operative functional, structural, and chemical neuroimaging findings known to be associated with centralized pain and indicative of CNS amplification are associated with the centralized pain phenotype and possibly predictive of failure to achieve pain relief after lumbar spine surgery. We acknowledge that these studies are exploratory and may be underpowered but feel that they will at a minimum provide critical preliminary data for future studies.

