
C. Sample size, statistical methods, and power calculation

Aim 1 Analyses: To demonstrate that common patient characteristics consistent with a centralized pain phenotype are associated with a patient's failure to derive benefit from lumbar spine surgery. **Analysis**

1a: Analgesic outcomes (AOC) for patients in the prospective cohort will be defined as "AOC-success" or "AOC-failure" for the purposes of further analyses. AOC-success is defined as those who demonstrate a 50% reduction in pain scores from baseline to 6 months, which would be a response more commensurate with the invasiveness of the intervention of spine surgery than a minimal clinically important difference score (MCID). FMness as measured by the 2011 FM Survey Criteria score⁶⁶ is the primary measure of interest and will be split by median score (and defined as FM-high and FM-low). Differences in surgical failure proportions (determined by pain score change as described above at 6-months) between the FM-high (n=50) and FM-low (n=50) groups will be tested using a two-sided chi-squared statistic at $\alpha=.05$. In addition to FMness, differences between AOC-success and AOC-failure groups for each of the constructs contained under the subheading "Comprehensive Phenotyping Battery" will be examined using appropriate parametric or non-parametric analyses. Furthermore, we wish to explore how multiple patient characteristics vary across these cohorts. A stepwise logistic regression model will then be fit to evaluate multivariate relationships. The analyses conducted in this aim will provide the candidate an opportunity to learn multivariate data analysis with advanced regression modeling as well as more familiarity with patient reported outcome measures. **Analysis 1b:**

Phenotypic differences between the AOC-failure group and the established-FBSS group will be examined using appropriate parametric or non-parametric tests to see if the longitudinally designated AOC-failure cohort is phenotypically similar in nature to the cross-sectional established-FBSS patients. We hypothesize that AOC-failure patients will appear similar to established-FBSS patients. The same comparisons will be explored for the longitudinally designated AOC-success group compared to the cross-sectional healthy controls group.

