Sample size for Study Procedures in Aims 1 and 2: We anticipate screening approximately 60 pre-operative lumbar spine surgery patients per year for possible enrollment into the study. Assuming a 50-60% recruitment rate, we estimate approximately 30-35 lumbar spine surgery patients enrolled per year during Years 1-4 of the award. This leads to an estimated total sample size of 100 lumbar spine surgery patients. We will also aim to recruit and enroll equal distributions of established-FBSS patients (n=50) and healthy controls (n=50). For the assumed effect size (population of 0.10 vs 0.50) and sample sizes (50 and 50 based on 2011 FM Survey Criteria score median split) and $\alpha=.05$ (two-sided) the power is 0.99. Several different assumptions were also explored. For example, if the assumed effect size is (population of 0.15 vs 0.45) or (population of 0.17 vs 0.43), then the respective power calculations are 92% and 82%, both which are adequate for significance purposes (e.g., >80%). The larger sample size will also be important for exploring multivariate models and potential subgroup analyses. The inclusion of healthy controls and established-FBSS patients will ensure adequate matching of gender and age to the patient cohorts for analyses.

Sample size for Study Procedures in Aim 3: We aim to recruit 30 lumbar spine surgery patients, 15 healthy controls, and 15 established-FBSS patients out of the total cohort to participate in the

neuroimaging study procedures. As this study is powered for the primary hypothesis in Aim 1, issues of power are of less concern for these investigatory neuroimaging studies.

D. Subject Criteria (See Vulnerable Populations appendix, if applicable):

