to malfunction. There is also a risk that metallic objects in or on the body may be heated by the radio frequency waves, possibly causing burns. Also, claustrophobia may be problematic, and individuals will be screened for this problem. Women of childbearing potential will be screened for pregnancy with a urine pregnancy test immediately before they go into the scanner. Finally, there exists a potential to cause peripheral nerve stimulation. Peripheral nerve stimulation is a light touching sensation on the skin surface, lasting only a few seconds. It may cause mild discomfort, but it is not harmful. The MRI machine is operated within FDA guidelines so the potential for inducing peripheral nerve stimulation is low. The MRI procedure is painless and not uncomfortable, although it does require the subject to lie still with the head and part of the body confined in a tunnel-like device. Evoked pain (QST) will be conducted during portions of the scanning and will have the same risks as those discussed in the "Physical Risks" section above. Other than those described above, there are no known biological risks due to exposure to the magnetic fields such as those that will be utilized in this study.

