Methods to reduce risks associated with QST (as conducted before and during MR/PET imaging) will include the following: a) the proposed settings and methods are widely used and have been shown to be safe in extensive use worldwide; b) participants are told that they are free to stop any testing procedure at any time; c) research personnel receive extensive training and follow detailed standardized operating procedures that ensure safety; d) the maximum pressures applied are set to be below levels that would cause tissue injury; e) the MAST and IPC-1000 automated pressure stimulators include redundant software, electrical, and mechanical safety features to ensure that the amount of pressure applied does not cause tissue damage, including a button that the patient or researcher can push to immediately release the device from his/her thumb; f) testing is automatically stopped if participants report maximal pain (e.g., 100 on 0 to 100 scale). During the performance of the MR, the volunteers will be monitored at all times by research personnel associated with the project (research assistant, radiology technologists) or the investigators themselves. Participants will be asked to complete and sign a safety screening form used by the KUMC Hoglund Brain Imaging Center and will be instructed to bring or wear clothing without metal fasteners, and remove jewelry and any other metal objects from their body. All people (including staff) who enter the exam room that contains the magnet are hand screened for magnetic material before entering. Participants will wear foam earplugs or headphones to reduce the loud noises made by the scanner. Participants will be able to communicate with the examiner throughout the scan. If needed, the participant can be removed immediately from the bore of the magnet. The MRI machine is operated within FDA guidelines so the potential for inducing peripheral nerve stimulation is low. Women of childbearing potential will be required to take a urine pregnancy prior to MRI testing. If refused, the participant will be excluded from any further aspects of the study. In addition, all the volunteers will have direct access to the phone numbers and pagers of the study coordinator and the responsible clinicians ([name]), as well as a 24-hour contact number (emergency room services). These phone numbers are provided in the consent forms. One copy of the signed consent form is provided to the subjects. They will be encouraged to contact the investigators if they notice any unusual symptoms or untoward side effects.

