Location where study will be performed: Study procedures including questionnaires and QST will take place at the KUMC Hoglund Brain Imaging Center in Kansas City, Kansas. For LSS patients participating in surveys only, consent & questionnaires may be provided in the resource room of the KUMC [name], Comprehensive Spine and Pain Management Center prior to the pre-op appointments. Brain Imaging Studies will be done at the Hoglund Brain Imaging Center. A subset of LSS patients (survey only), Healthy Controls, and Failed Back Surgery Syndrome participants will perform their baseline surveys at home following a remote eConsent. Follow up questionnaires (LSS only) will be done via phone-call or via email depending on convenience for the patient.

G. Personnel who will conduct the study, including:

1. Indicate, by title, who will be present during study procedure(s): PI, Study Coordinator, Research Assistant
2. Primary responsibility for the following activities, for example:
 - a. Determining eligibility: Study Coordinator, Research Assistant, PI
 - b. Obtaining informed consent: PI, study coordinator, research assistant, or rotating research medical students
 - c. Providing on-going information to the study sponsor and the IRB: PI
 - d. Maintaining participant's research records: PI, Study Coordinator, Research Assistant
 - e. Completing physical examination: N/A
 - f. Taking vital signs, height, weight: N/A
 - g. Drawing / collecting laboratory specimens: N/A
 - h. Performing / conducting tests, procedures, interventions, questionnaires: PI, study coordinator, research assistant or rotating research medical students
 - i. Completing study data forms: PI, study coordinator, or research assistant
 - j. Managing study database: Study Coordinator & KUMC Department of Biostatistics

H. Assessment of Subject Safety and Development of a Data and Safety Monitoring Plan

1. Persons/groups who will review the data (study team; independent safety monitor, data monitoring committee or formal DSMB): Study team
 - a. Data/events that will be reviewed: All study data, procedures, and any events
 - b. Frequency of review: As needed
 - c. Types of analyses to be performed: No interim analyses planned
 - d. Safety-related triggers that would cause the PI to stop or alter the study: None expected.

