7. This study will also use Qualtrics electronic data capture system. Survey distribution is through a personalized link specific to the patient that is sent to the patient's email address (security whitepaper for Qualtrics uploaded to eIRB application documents).
8. Discuss any use of mobile devices for data collection or storage. N/A
9. Discuss security measures if identifiable data are sent outside KUMC. N/A

B. Sample / Specimen Collection: N/A

C. Tissue Banking Considerations: N/A

- D. Procedures to protect subject confidentiality:** Several measures have been taken to reduce the risk of breach of confidentiality. These include training of study team members, electronic and physical security measures for data capture and storage, and collecting a minimum of identifiable information for each individual participant. The study team will take all possible steps to protect the privacy of subjects. This includes:
- Maintenance of protected health information (PHI) will include the assignment of a coded participant ID that will be used for accessing and merging of all records.
 - Participant's data and specimens will be coded (assigned a unique study number) which will allow the researchers to link the data/specimens to other information that are provided through questionnaires and other study activities
 - The code key linking the participant to their unique study number will be maintained via RedCap. The key will only be used to connect other study information to the data/specimens. This code will never leave the University of Kansas Medical Center.

A breach of confidentiality will be considered a serious adverse event. As such, it will be reported to the University of Kansas Medical Center IRB within 5 days of occurrence per University policies and procedures, and a remediation plan will be put in place immediately.

E. Quality Assurance / Monitoring

1. Describe steps to be taken to assure that the data collected are accurate, consistent, complete and reliable. (source data verification, audits or self – assessment) Self-assessment.
2. Describe whether there are plans to have ongoing third party monitoring. N/A

V. Data Analysis and Reporting

A. Statistical and Data Analysis: Refer to section 2.C.

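### Declining the pre-MRI pregnancy test ends all study participation, so an imaged surgical patient would lose her 6-month outcome; the loss is small and avoidable by rewording

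*Combined protocol and SAP*

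**What the plan says.** The protocol mentions the test twice, both times under Risk/benefit assessment in Section II.E. The paragraph on MRI risks states: "Women of childbearing potential will be screened for pregnancy with a urine pregnancy test immediately before they go into the scanner". The paragraph on reducing risks repeats the requirement ("Women of childbearing potential will be required to take a urine pregnancy prior to MRI testing") and then gives the consequence: "If refused, the participant will be excluded from any further aspects of the study".

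Four other parts of the plan determine what that consequence means:

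- **Who is scanned.** Overall Study Design (II.B): "Patients for Aim 3 will be recruited from both the prospective and cross-sectional cohorts enrolled for Aims 1 and 2". Section II.C gives the numbers: "We aim to recruit 30 lumbar spine surgery patients, 15 healthy controls, and 15 established-FBSS patients out of the total cohort". Imaging of surgical patients is pre-operative.
- **What the primary analysis needs.** Section II.C: "AOC-success is defined as those who demonstrate a 50% reduction in pain scores from baseline to 6 months".
- **Eligibility and withdrawal (II.D).** Pregnancy or nursing excludes any participant, and the criteria are headed as self-reported. The investigator withdraws anyone who develops an exclusion criterion. Declining the test is not a listed criterion.
- **Specimens.** Personnel item g in II.G reads "Drawing / collecting laboratory specimens: N/A", and item B under Data Collection and Protection reads "Sample / Specimen Collection: N/A". Personnel item h gives the PI, coordinator, research assistant or rotating medical students responsibility for tests and procedures. The study schedule has no row for a pregnancy test.

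**The concern.** The test is a condition of entering the scanner, but declining it costs the participant everything that remains in the study. Her questionnaires and 6-month pain score do not depend on the scan or the test, so the plan would discard an outcome it could have collected.

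The rule also sits oddly with the rest of the protocol. A participant may stop the imaging, stop any testing procedure, or leave any question unanswered, and no removal from the study is attached to any of these. Surgical patients who are not imaged stay in on self-reported pregnancy status and are never tested.

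Three things are at stake: losing primary outcomes from women only, in a study whose own text says centralized pain is commoner in women; losing them from a sample size with no stated dropout allowance; and a financial penalty for declining a scan-day test.

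**Working it through.** **1. Which participants can lose an outcome.** Sixty people are scanned: 30 surgical patients, 15 controls and 15 established-FBSS patients. The last two groups complete the questionnaire battery once, so only the 30 surgical patients have a 6-month outcome to lose. The remaining 100 − 30 = 70 surgical patients never meet the rule. The schedule key defines the imaged surgical group as phenotyping plus QST plus imaging, so the same 30 fall within the 50 surgical patients with QST, and a loss counts in Aim 2 as well.

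**2. Expected number lost.** The documents give neither the share of childbearing potential nor a refusal rate, so both are assumptions.

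- Women among the 30: 30 × 1/2 = 15 (II.D aims for roughly equal numbers of men and women)
- Of childbearing potential: 15 × 1/3 = 5 to 15 × 1/2 = 7.5
- Refusing at 5% to 20%: 5 × 0.05 = 0.25 to 7.5 × 0.20 = 1.5

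That is about 0 to 2 patients: 0.25% to 1.5% of the Aim 1 cohort of 100, and 0.5% to 3% of the Aim 2 surgical cohort of 50.

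**3. The plan's own power.** With n per group, two-sided α = 0.05 and p̄ the mean of p1 and p2:

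power = Φ{ [ |p1 − p2| − 1.96 √(2 p̄(1 − p̄)/n) ] / √( [p1(1 − p1) + p2(1 − p2)]/n ) }

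For 0.17 v 0.43 and n = 50, p̄ = 0.30. The numerator is 0.26 − 1.96 × √0.0084 = 0.26 − 0.1796 = 0.0804. The denominator is √0.007724 = 0.0879. The ratio is 0.914, so power is 0.820. The same formula gives 0.996 for 0.10 v 0.50 and 0.918 for 0.15 v 0.45. The plan states 0.99, 92% and 82%, so its figures reproduce.

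**4. Power after k losses**, split evenly, n = (100 − k)/2 per group:

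| k | 0.10 v 0.50 | 0.15 v 0.45 | 0.17 v 0.43 |
|---|---|---|---|
| 0 | 0.996 | 0.918 | 0.820 |
| 1 | 0.996 | 0.915 | 0.816 |
| 2 | 0.996 | 0.912 | 0.812 |
| 5 | 0.995 | 0.904 | 0.799 |
| 8 | 0.993 | 0.894 | 0.786 |

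If two losses both came from one FM group, power in the weakest scenario would be 0.811 or 0.812, depending on the group. The row k = 8 is the extreme in which every woman facing the rule (7.5, rounded up) refuses.

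**5. Payment.** A surgical patient with QST receives $100 for the pre-operative visit, then $10 + $15 + $25 + $50 = $100 over follow-up, $200 in all. The rule costs her the second $100. The separate $100 imaging payment goes only to those who take part in imaging, so she would lose it under any rule.

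**The case against.** The strongest defence is that pregnancy is an exclusion for everyone, not only for MRI, and that developing an exclusion criterion leads to withdrawal. On that structure, a whole-study consequence for leaving pregnancy status unresolved is coherent. This stands in part: the refusal rule cannot be reworded alone. If it were, a woman who tested positive would still be withdrawn from the whole study while one who declined would continue, which is a new inconsistency and an incentive to decline. It does not justify the rule, because refusal is not pregnancy and the 70 unscanned surgical patients are accepted on self-report.

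It is also fair to say that the sentence does not name the 6-month outcome or say whether data already collected are kept. Loss of the outcome is inferred from the breadth of the wording, though no narrower reading is offered.

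A reader might infer more than the documents support:

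- **That nobody is assigned the test.** Personnel item h gives named roles general responsibility for tests and procedures, and the risk section fixes when the test is done. The entry under Data Collection and Protection sits next to tissue banking and can be read as research samples. The schedule lists forms and questionnaires rather than each procedure. These are clerical mismatches and do not show that the test would be skipped.
- **That a stated fetal-risk safeguard is in doubt.** The text names no fetal risk.
- **That the primary comparison is biased or underpowered.** Loss confined to women is selective, but nothing shows that refusal is related to outcome within the FM-high or FM-low group, and the numbers are too small to matter for power.

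**Conclusion.** The point holds in a limited form. As written, the rule removes a refusing surgical patient from the imaging subset before her 6-month outcome, and costs her $100 in follow-up payments, for declining a test that only the scan requires. It reaches at most the women of childbearing potential among 30 of the 100 surgical patients. The expected loss of about 0 to 2 patients rests on the assumed childbearing-potential share (a third to a half) and refusal rate (5–20%), and on half of those imaged being women. Within that range power falls by at most 0.8 points in the weakest scenario (0.820 to 0.812); power drops just below 80% there only at about five losses. The case for change is that the loss is avoidable, confined to women and out of line with how the protocol treats other refusals. It is a low-priority change worth making.

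**What to change.** In the risk-reduction paragraph, limit the consequence of refusal to imaging: a participant who declines the test will not undergo MRI, while questionnaires, QST already completed and all follow-up continue. In the same amendment, reconcile this with the all-participant pregnancy exclusion and the withdrawal rule in II.D, so that the consequences of declining the test and of a positive result are both stated and consistent. State also what happens to data already collected.

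As housekeeping, align the two specimen entries with the required test, add it to the schedule for the imaged groups, and name the role that performs and records it.

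The cost is a short amendment touching a few linked passages. No one is scanned without a test, so the requirement before MRI is unchanged. The imaging data of those who decline are lost under either rule.
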